1.2 Rationale

The purpose of this study is to evaluate the long-term (up to approx. 10 years after primary series for PrEP) persistence and to assess the boostability of immune responses in subjects who participated and completed V49_23 study and received either the full primary vaccination series according to the conventional rabies plus JE (Conv-R/JE), or the accelerated rabies plus JE (Acc-R/JE), or the conventional rabies (Conv-R) PrEP alone regimens.

2.0 OBJECTIVES

2.1 Primary Objectives

Immunogenicity Objectives

3. To compare the long-term (up to approx.10 years) persistence of antibody responses (i.e. time until antibody concentrations drop below 0.5 IU/mL) in subjects who received a primary series of accelerated or conventional rabies PrEP intramuscular (IM) regimen in the parent study V49_23.
4. To evaluate the antibody responses to a booster dose of PCEC rabies vaccine administered to subjects with RVNA concentrations <0.5 IU/mL following a primary series of accelerated or conventional rabies PrEP IM regimen in the parent study V49_23.

Safety Objective

To evaluate the safety of a booster dose of PCEC rabies vaccine following a primary series of accelerated or conventional rabies PrEP IM regimen in the parent study V49_23.

2.2 Secondary Objective

Immunogenicity Objective:

To evaluate the long-term (up to approx.10 years) immunogenicity in subjects who received a primary series of accelerated or conventional rabies PrEP IM regimen in the parent study V49_23.

3.0 STUDY DESIGN

3.1 Overview of Study Design (Amended 25 February 2019)

Introduction of study design:

This is a phase 3, open-label, multicenter, extension of V49_23 study in adult subjects.

In the parent study (V49_23) subjects from ≥ 18 years to ≤ 65 years of age were randomized to one of four vaccination groups, three of which for rabies pre-exposure prophylaxis according to conventional (1.0 mL dose of PCEC rabies vaccine administered IM on each of days 1, 8 and 29) alone or in combination with Japanese Encephalitis (JE) vaccination or according to a new, one-week, accelerated (1.0 mL dose of PCEC rabies vaccine administered IM on each of days 1, 4 and 8) regimen in combination with JE vaccination depending on the study group (see Table 3.1-1).

Subjects who were randomized into one of the 3 rabies vaccination group regimens, who received the full PrEP rabies regimen and completed V49_23 following study protocol will be invited to take part to this study.

Subjects who were randomized to the JE conventional group in V49_23 study will not be invited to take part to this extension study.

Table 3.1-1 Vaccine Groups in Studies V49_23 and V49_23E1

V49_23 study		V49_23E1 study	
Study Vaccine Group	Regimen of Primary Vaccine Administration N of subjects who received full PrEP and completed the study	Study Vaccine Group Maximum N of subjects who will be invited for enrollment (at the start of the extension study)	Regimen of Booster Vaccination
Conventional Rabies with concomitant JE vaccination (Conv-R/JE)	Rabies PrEP Days 1, 8 and 29 JE primary series Days 1 and 29 N=158 subjects	Conv-R/JE N= up to 158 subjects	A single PCEC rabies booster dose (1.0 mL) IM for subjects with RVNA concentrations <0.5 IU/mL
Accelerated Rabies with concomitant JE vaccination (Acc-R/JE)	Rabies PrEP Days 1, 4 and 8 JE primary series Days 1 and 8 N=209 subjects	Acc-R/JE N= up to 209 subjects	A single PCEC rabies booster dose (1.0 mL) IM for subjects with RVNA concentrations <0.5 IU/mL

V49_23 study		V49_23E1 study	
Conventional Rabies vaccination alone (Conv-R)	Rabies PrEP Days 1, 8 and 29 N=211 subjects	Conv-R N= up to 211 subjects	A single PCEC rabies booster dose (1.0 mL) IM for subjects with RVNA concentrations <0.5IU/mL
Conventional JE vaccination alone (Conv-JE)	JE primary series Days 1 and 29 N=52 subjects	NA	NA

Up to 578 subjects, who completed rabies PrEP regimens in the parent study V49_23 will be invited to participate to this extension study.

All sites will be trained in a uniform fashion and **those** sites will be monitored to ensure consistency in study execution across all centers.

Informed consent will be performed prior to any study-related procedures.

Subjects who sign the informed consent will be screened to assess for their eligibility of participation in the study.

All individuals who are screened for the study, as defined in this section, should be recorded on the “subject screening log” where information on the selection of potential participants in the trial should be collected. The reason why an individual was not enrolled, the enrollment date and assigned subject number and code which is carried over from the parent study, should be recorded by the investigator/study staff. It is the responsibility of the investigator/delegate to file this document among those of the Investigator Site File to be readily available for on-site monitoring and/or for inspection by the relevant authorities.

Subjects will receive their booster doses based on their own antibody concentrations (booster will be administered only to those subjects with RVNA concentrations <0.5 IU/mL), medical history and physical examination to ensure that they are in good health according to the investigator’s opinion and meet all inclusion criteria and none of the exclusion criteria.

For all subjects enrolled there will be overall 8 blood draws (of approximately 7 mL each) scheduled during the course of the extension study; each of these blood draws will be taken at each Scheduled Clinic Visit, from extension study Day 1 (Year 3 after completion of PrEP in the parent study V49_23) and then yearly through Year 10. During

Scheduled Clinic Visit and Additional Clinic Visit, subjects will be observed for at least 15 minutes after the blood draw for any adverse event (AE).

A urine pregnancy test will be performed for female subject of childbearing potential who are eligible to receive the booster dose prior to vaccination.

Vaccination procedures:

Only those subjects for which the RVNA concentration determined to be <0.5 IU/mL based on the blood sample from Visit 1, 2, 3, 4, 5, 6, and 7 (i.e., on Year 3, 4, 5, 6, 7, 8, and 9) will receive the booster dose of rabies vaccine in an open label fashion, time of each booster dose and blood draw for rabies antibody concentrations needs to be meticulously recorded.

If, after having received a booster dose, the subject does not reach the adequate antibody concentration of 0.5 IU/mL at two consecutive determinations, neither at 7 days after the booster dose (i.e. Additional Clinic Visit) nor at the next yearly evaluation (i.e. Scheduled Clinic Visit), an additional booster dose may be administered at the following Ad hoc Clinic Visit. ***If the subject is still non-responder, subsequent management should be at the discretion of the investigator.***

Should a subject have RVNA concentrations below 0.5 IU/mL at blood draw performed at the final Scheduled Clinic Visit (Year 10), the ***investigator will invite the subject*** to receive a booster dose of the rabies vaccine outside the study following standard clinical practice and there will be no further analyses performed on this additional vaccination.

Such subject will receive 1.0 mL single dose (freeze-dried powder + diluent [sterile water]) for reconstitution and injection of the rabies vaccine intramuscularly.

Post-vaccination evaluations:

The safety data will be collected only from those subjects who received booster dose of rabies vaccine during any Ad hoc Clinic Visit.

The safety data in these subjects will include;

- At least 30 minutes post-vaccination: ***the subject will be observed by the investigator/delegate at the clinical trial site for any immediate reaction and it will be documented in subject's source document.***
- Starting from the time of booster administration until ***completion of safety follow-up period (the day of the next Scheduled Clinic Visit after booster vaccination or on the date of Early Termination Visit, whichever is earlier)*** SAEs and the associated

concomitant medications will be recorded by interviewing the subject during next *Clinic Visit* and based on the subject's medical records.

To investigate the prompt boostability of the immune response, during Additional Clinic Visits additional blood samples will be drawn approximately 7 days after the booster dose only from those subjects who received PCEC rabies booster vaccine during previous Ad hoc Clinic Visits.

In order to understand complete evolution of the antibody decay over time and the effect of the booster dose, every year, an immunogenicity and safety analysis will be carried out and the results will be stored in the internal clinical data repository.

Two Clinical Study Reports (CSR) are planned:

- One interim CSR will be released after all subjects will complete Scheduled Clinic Visit 4 (i.e. Year 6). This CSR will include both immunogenicity and safety analyses halfway through the study. The interim CSR might be submitted to the Health Authority in case results support indication for the booster dose at a given time after the primary regimen.
- The final CSR will be released at the completion of the study and will include all study data from Visit 1 (Year 3) to Visit 8 (Year 10).

A listing with individual subject antibody titers will be generated by the sponsor to show which subjects have rabies neutralizing antibody concentrations <0.5 IU/mL and thus qualify to be vaccinated with a booster dose of rabies vaccine during the Ad hoc Clinic Visit. The decision will be based on RVNA concentration from the blood sample taken in the previous Scheduled Clinic Visits (e.g. booster administration at the Ad hoc Clinic Visit 1.1 for subjects with RVNA concentrations ***<0.5 IU/mL at the Scheduled Clinic Visit 1***).

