Study Event	References														

^a Ad hoc Clinic Visit (which is planned to occur as soon as the results of the antibody assay will be available and within approximately **6 to 9** months from the blood draw taken during a previous “Scheduled Clinic Visit”) is only applicable for those subjects with RVNA concentrations <0.5 IU/mL during this extension study. See [sections 3.1](#) and [3.9](#) for further details.

^b Additional Clinic Visit (within approximately 7 days from Ad hoc Clinic Visit) only applicable for subjects who will receive a booster dose of PCEC rabies vaccine during Ad hoc Clinic Visit.

^c Procedure to be performed prior to vaccination. *Physical exams have to be done by practitioners in accordance with their institutional policy. Should the physical assessment reveal any abnormal values or events, which fall under definition of SAE, these must be documented in the CRF Adverse Events Form and reported to sponsor.*

^d Only for female subject of childbearing potential who are eligible to receive the booster dose.

^e **GSK Biologicals' Randomization System on Internet (SBIR) will be used for Treatment allocation.**

^f SAEs and the associated concomitant medications will be collected starting from the booster administration until the *completion of safety follow-up period (the day of the next Scheduled Clinic Visit after booster vaccination or on the date of Early Termination Visit, whichever is earlier)*.

LIST OF ABBREVIATIONS (Amended 25 February 2019)

AE	Adverse Event
CBER	Center for Biologics Evaluation and Research
CCEEVs	Cell Culture or Embryonated Egg-Based rabies Vaccines
CI	Confidence Interval
CRO	Contract Research Organization
CSR	Clinical Study Report
e CRF	electronic Case Report Form
EC	Ethic Committee
EDC	Electronic Data Capture
EMA	European Medicines Agency
FAS	Full Analysis Set
FDA	U.S. Food and Drug Administration
GCP	Good Clinical Practices
GMC	Geometric Mean Concentration
GMR	Geometric Mean Ratio
HR	Hazard Ratios
ICF	Informed Consent Form
ICH	International Conference for Harmonisation of Technical Requirements for Pharmaceuticals for Human Use
ID	Identification (Subject ID)
IM	Intramuscular
IRB	Institutional Review Board

IU	International Unit
KM	Kaplan-Meier
MedDRA	Medical Dictionary for Regulatory Activities
mg	Milligram
mL	Milliliter
PCEC	Purified Chick-Embryo Cell Culture
PEP	Post Exposure Prophylaxis
PrEP	Pre-Exposure Prophylaxis

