7.1.2 Unsolicited Adverse Events

An unsolicited adverse event is an AE that was not solicited and that was spontaneously communicated by a subject or legal guardian who has signed the informed consent. In this study only SAEs and the associated concomitant medications following PCEC rabies booster vaccinations ***will be collected***, starting from the time ***the subject receives the booster dose until completion of safety follow up period, which is, the day of the next Scheduled Clinic Visit after booster vaccination or on the date of Early Termination Visit, whichever is earlier*** (see [section 7.1.4, Serious Adverse Events](#) and [section 7.1.5](#),

Methods for Recording Adverse Events and Serious Adverse Events), based on the subject's interview during Clinic Visit. SAEs collected during physical exams at Scheduled and Ad hoc visits will be as well collected.

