7.1.5 Methods for Recording Adverse Events and Serious Adverse Events

All findings in subjects experiencing SAEs and any medication or other therapeutic measures used to treat the SAE in addition to the outcome of the SAE after PCEC rabies booster dose or collected during physical exams at Scheduled and Ad hoc visits, must be reported both on the VSAE Report Form which is part of the Investigator Site File and in the eCRF.

Investigator must report those events to his/her corresponding EC or applicable regulatory authorities in accordance with institutional policy/regulatory requirements and adequate documentation of this notification must be provided to the Sponsor. During the course of the study, all SAEs which occur from the time of booster administration until completion of safety follow-up period (the day of the next Scheduled Clinic Visit after booster vaccination or on the date of Early Termination Visit, whichever is earlier), whether considered to be associated with the study vaccination or not, must be reported within 24 hours of the site becoming aware of the event to GSK or its designee. Specific instructions and contact details for collecting and reporting SAEs to GSK will be provided to the investigator.

After receipt of the initial report, representatives of GSK or its designee will contact the investigator if it is necessary to obtain further information for assessment of the event.

GSK or its designee must also comply with the applicable regulatory requirement(s) related to the reporting of suspected unexpected serious adverse vaccine reactions (also known as SUSARs) to the regulatory authorities and the IRB/EC. If a SUSAR or other safety signal relating to use of one of the study vaccines is reported to GSK or its designee, the Sponsor will communicate the information to the investigator and the investigator will be responsible for submitting this information to the EC and other relevant authorities.

All SAEs will be evaluated by the investigator for relationship of the event to study vaccine. SAEs that are judged to be possibly or probably related to the study vaccine should be reported to the Sponsor as related/suspected events, *irrespective of time frame of SAEs reporting.*

The relationship of the study vaccine to a SAE will be determined by the investigator based on the following definitions:

1. Related/suspected

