8.4.2.1.3 Analysis of Unsolicited Adverse Events (Amended 25 February 2019)

This analysis applies to all **SAEs** occurring during the study, judged either as probably related, possibly related, or not related to vaccination by the investigator, recorded in AE CRF, with a start date on or after the date of booster dose. SAE starting prior to booster dose will not be recorded. The original verbatim terms used by investigators to identify adverse events in the CRFs will be mapped to preferred terms using the MedDRA

dictionary. The serious adverse events will then be grouped by MedDRA preferred terms into frequency tables according to system organ class.

All reported serious adverse events, as well as serious adverse events judged by the investigator as at least possibly related to study vaccine, will be summarized according to system organ class and preferred term within system organ class. When a serious adverse event occurs more than once for a subject, the maximal severity and strongest relationship to the vaccine group will be counted.

Separate summaries will be produced for the following categories:

- Serious adverse events.
- Serious adverse events that are possibly or probably related to vaccine.
- Serious Adverse event leading to withdrawal.
- Deaths

Data listings of all serious adverse events will be provided by subject. In addition, serious adverse events in the categories above will be provided as listed data.

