All further subject immunogenicity data will not be used for Time to event analysis.

GMC and percentage analysis - boostability:

Subject is included in the Exposed to Booster Set and independently on time or visit in which booster is administered the time-points will be as following:

- Pre-booster
- 7 days after booster
- 6 to 9 months after booster

Long-term persistence of antibody responses after primary series

All immunogenicity data until booster will be part of analysis as they are reported.

For subjects receiving a booster dose, the following method of imputation will be used for antibody values:

- Values, missing or not, will be replaced with half of the quantification level (0.1 IU/mL) from that moment onward.

Subjects receiving a booster dose outside of the study and for which RVNA value at the time of booster vaccination is not available will be excluded from FAS-2 and PPS-2 (see section 7.3 for details)

Duration in the Study

Duration in the study is defined in days as:

Last visit date (visit x)^a – Enrollment date (visit 1) + 1

^a or premature discontinuation date (in case of withdrawal from the study)

The duration is missing if one of the dates is missing or incomplete.

Unsolicited Serious Adverse Events

All serious adverse events (AEs) following *Rabipur* booster dose within the study will be characterized according to the date of occurrence related to the vaccination phase as follows:

- **Emergence before vaccination phase:** start date before the first date of injection of study vaccine.
- **Emergence during vaccination phase:** start date on or after the first date of injection of study vaccine or, adverse event increase in severity including to “serious” AE.

If start date is equal to the first date of injection then “timing” variable (“On injection day, before injection”/“On injection day, after injection”) will be used to define whether the adverse event occur before or after the injection.

If an AE start date is missing or unknown, the AE will be considered as emergent.

When start and/or end dates of an AE are only partially known, AEs will be categorized as emergent before, during, or after vaccination phase using the following rules:

- If the partial end date is before ($<$) the first study vaccination (i.e., year or year & month is/are before the first study vaccination year or year & month) then the AE is emergent before vaccination phase.

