- If the partial start date is equal or after (\geq) the first study vaccination (i.e., year or year & month is/are after or the same as the first study injection year or year & month) then the AE is emergent during vaccination phase.

The **maximum event severity** is the greatest severity associated with a preferred term (PT) for a reported AE according to the following order: Mild < Moderate < Severe. Unknown/ Missing severity is considered as severe (except for the definition of emergence).

Multiple AEs with the same PT for the same subject are counted only once.

Vaccination-related AEs are those for which the cause has been evaluated by the investigator, and recorded either as possibly related, probably related or unknown/ missing.

Pre-study, Concomitant and Post-Vaccination Medications

A **prior medication** is a medication received by the subject prior to the start of V49_23E1 (i.e. Termination visit date for V49_23 \leq medication start date $<$ start of this extension study V49_23E1).

A **concomitant medication** will include drugs (antipyretics and/or analgesic medications within 24 hours prior to vaccination) and all medications (including vaccines) from the time of the boost per administration until the day of next Scheduled Clinic Visit. (i.e. medication start date \geq booster administration date).

Concomitant medications, as defined in study protocol, include all medications (including vaccines) taken by/administered to subjects who experienced Serious Adverse Events (SAEs) during the safety follow up period (which is, the day of the next Scheduled Clinic Visit after booster vaccination or the date of Early Termination Visit, whichever is earlier) after administration of the rabies vaccine booster dose. In case of start date of a medication intake is missing, the medication is considered as concomitant.

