13.3. Unsolicited Adverse Events

This analysis applies only to SAEs occurring during the study and from the time of booster injection till the next Scheduled Clinic Visit (approximately 6 months after booster administration), judged either as probably related, possibly related, or not related to vaccination by the investigator, recorded in AE electronic Case Report Form (eCRF), with a start date on or after the date of booster dose. SAE starting prior to booster dose will not be recorded in the eCRFs.

The original verbatim terms used by investigators to identify SAEs in the CRFs will be mapped to PTs using the MedDRA dictionary. The SAEs will then be grouped by MedDRA PTs into frequency tables according to system organ class. SAEs judged by the investigator as at least possibly related to study vaccine will be summarized by vaccine group, according to system organ class and PT within system organ class. When an unsolicited SAE occurs more than once for a subject, the maximal severity and strongest relationship to the vaccine group will be counted.

Separate summaries will be produced for the following categories:

- Serious adverse events.
- Serious adverse events that are possibly or probably related to booster vaccination.
- Serious adverse event leading to withdrawal.
- Deaths

Data listings of all SAEs will be provided by subject. In addition, SAEs in the categories above will be provided as listed data. Only vaccine-emergent SAEs (see section 8.8 for definition) will be analyzed, i.e., excluding those eventually occurring after a subject has given informed consent but before booster vaccination.

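### The protocol both bars and requires recording of SAEs found at pre-booster physical exams, and the SAP 8.8 date rules can count incompletely dated ones as booster SAEs

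*Protocol*

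**What the plan says.** **Texts that restrict recording.**
- Protocol 3.1, under post-vaccination evaluations: "The safety data will be collected only from those subjects who received booster dose of rabies vaccine during any Ad hoc Clinic Visit".
- Protocol Table 2a footnote b limits SAE collection to boosted subjects, from the time of the booster. Protocol 7.1.4 says only SAEs following a booster are collected.
- Protocol 8.4.2.1.3: "SAE starting prior to booster dose will not be recorded". SAP 13.3: "SAE starting prior to booster dose will not be recorded in the eCRFs".

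**Texts that require more.**
- Protocol 7.1.2 first limits collection to post-booster SAEs, then adds: "SAEs collected during physical exams at Scheduled and Ad hoc visits will be as well collected".
- Protocol 7.1.5 joins a second stream to the post-booster SAEs with the word 'or': findings "collected during physical exams at Scheduled and Ad hoc visits, must be reported both on the VSAE Report Form" and also in the eCRF.
- Protocol 5.1.2, Table 2a footnote d and Table 2b footnote c send an exam finding that meets the SAE definition to the AE CRF and the sponsor.
- Table 2a schedules the exam for all subjects at all eight Scheduled visits. For the Ad hoc exam, Table 2b footnote c says: "Procedure to be performed prior to vaccination".

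**How the SAP classifies what is recorded.** SAP 13.3 analyses only vaccine-emergent SAEs as defined in SAP 8.8, and it asks for a start date on or after the booster. SAP 8.8 says: "If an AE start date is missing or unknown, the AE will be considered as emergent". A partial start date makes the event emergent when its "year or year & month is/are after or the same as the first study injection year or year & month". A partial end date before the first injection makes the event pre-vaccination.

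**The concern.** The collection rules conflict for two kinds of event: an SAE found at the annual exam of an unboosted subject, and an SAE found before the injection in a subject who is then boosted. In Table 2a, footnotes b and d give opposite instructions for the same unboosted subject.

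The second kind of event reaches the analysis. Counting an SAE of unknown date as emergent is a sound conservative default when its timing is truly unknown. Here the timing can be known: an event found at an exam before the injection began before the injection. SAP 8.8 has no rule that uses the date of the visit at which the event was found.

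At stake is the primary safety summary, the number and percentage of SAEs after the booster. No solicited events are collected and non-serious events stay in source documents, so SAEs are the only safety outcome tabulated. One wrongly counted event could be visible.

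**Working it through.** The documents give no figure to reproduce. The check applies the SAP 8.8 rules to an SAE that truly starts before the booster in a subject who is later boosted.

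**1. What the rules return**

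| Start date | End date | Class under SAP 8.8 |
|---|---|---|
| Complete, before injection | any | Before vaccination (correct) |
| Missing | none placing it before the injection | Emergent (wrong) |
| Partial, same year or year and month as injection | none placing it before the injection | Emergent (wrong) |
| Partial | partial, before injection | Before vaccination (correct) |

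The before/after-injection timing variable applies only when the start date equals the injection date, so it does not help in the second and third rows.

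*Example.* An SAE is found at a February Scheduled exam, with onset recorded as the year only and still ongoing. The booster follows in September, within the 6 to 9 months allowed. The onset year equals the injection year, so the event is classed as emergent, although the February exam shows that it came first. A recorded end date of March that year would have excluded it.

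**2. How often a partial date is caught** (visit dates assumed uniform over a 365-day year; no end date placing the event before the booster)

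*Found at the Scheduled exam, onset close to the exam, year only, booster m months later.* The event is emergent if exam and booster fall in the same calendar year, a share of about (12 − m)/12:
- m = 6: 6/12 = 50%
- m = 7: 5/12, about 42%
- m = 8: 4/12, about 33%
- m = 9: 3/12 = 25%

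Day-by-day enumeration gives 49.6%, 41.4%, 32.9% and 24.7%. With onset 30 days before the exam the shares are 41.4% (6 months) and 16.4% (9 months). With onset 90 days before, they are 24.9% and 0%.

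*Found at the Ad hoc exam on the booster day, onset L days earlier, year only.* The share is (365 − L)/365:
- L = 7: 358/365 = 98.1%
- L = 30: 335/365 = 91.8%
- L = 90: 275/365 = 75.3%

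*Same, with year and month known.* The share is the sum over months of max(0, days in month − L), divided by 365:
- L = 7: (365 − 12 × 7)/365 = 281/365 = 77.0%
- L = 14: (365 − 12 × 14)/365 = 197/365 = 54.0%
- L = 30: only the seven 31-day months contribute, 7/365 = 1.9%

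*Missing start date:* 100%.

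These shares are conditional on an event of this kind with an incomplete date. They are not event rates.

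**3. Effect on the table.** Each misclassified event adds 1/n, where n is the number boosted. The documents do not give n, so the range is by assumption:
- n = 50 (for example, one regimen): 1/50 = 2.0 points
- n = 150: 1/150 = 0.7 points
- n = 578, the ceiling if every invited subject were boosted (158 + 209 + 211): 1/578 = 0.2 points

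If 3 of 150 boosted subjects had a true post-booster SAE (also assumed), one extra event moves 3/150 = 2.0% (Clopper-Pearson 95% CI 0.4 to 5.7) to 4/150 = 2.7% (0.7 to 6.7).

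**The case against.** The case on the other side is substantial.

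- **The SAP has filters.** A reader might infer that the SAP takes pre-booster records to be absent and leaves them unhandled. Its sentence that they will not be recorded points that way, but the same section says that SAEs between consent and booster are excluded and asks for a start date on or after the booster. SAP 8.8 has a pre-vaccination class. This stands. What remains is that an event with a missing date cannot meet the start-date condition in 13.3, yet 8.8, to which 13.3 defers, calls it emergent. The SAP therefore conflicts with itself.
- **The end-date rule catches some events.** This stands for partial end dates. The SAP does not say how a complete end date is used when the start date is incomplete, nor which rule takes precedence. The working gives it the benefit of the doubt.
- **Such events should be rare.** SAEs go on a dedicated form with sponsor follow-up and data queries, so an onset may seldom stay incomplete. The booster criteria also require good health, so an active serious condition may mean no booster. Both points lower the likely count. Neither changes what the rule does when such a record exists.
- **The 3.1 sentence stands under post-vaccination evaluations**, and 3.4.1 does not say 'only'. Both are fair. The conflict does not depend on them: 7.1.4, Table 2a footnote b and 8.4.2.1.3 are explicit.
- **Site reporting.** A reader might infer that sites do report differently according to the section they follow. The text permits this, but sites are to be trained uniformly and the documents do not show that it happens.

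**Conclusion.** The point holds as a contradiction in the collection rules and a gap in a derivation rule. Only SAEs that meet all of these conditions can be miscounted:
- found at an exam before the injection;
- in a subject who is later boosted;
- with a missing start date, or a partial one matching the injection's year or year and month;
- with no end date placing the event before the booster.

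For such an event, SAP 8.8 gives a result that the date of the detecting exam disproves.

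A reader might go further and infer that the primary safety result is materially biased, or that SAEs of unboosted subjects leak into it. The documents do not support either. Fully dated events are classified correctly, and never-boosted subjects fall outside the Safety Set (SAP 7.5) and the safety analysis (SAP 8.2.1). For them only the collection conflict applies. The number of affected events is not given and cannot be computed; it is probably small. The percentages above rest on assumed numbers of boosted subjects and SAEs, and the calendar shares on evenly spread visit dates. The change is worth making because it is cheap and serves the exclusion that SAP 13.3 already intends.

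**What to change.** 1. Reconcile protocol 3.1, Table 2a footnotes b and d, Table 2b footnote c, 5.1.2, 7.1.2 (including its internal conflict), 7.1.4 and 7.1.5. One rule should state whether exam-found SAEs are collected in unboosted subjects and before the booster, and whether they enter the clinical database. Protocol 7.1.6 shows one alternative: pregnancy-outcome SAEs in unboosted subjects go on the VSAE form but stay out of the database. Correct protocol 8.4.2.1.3 and SAP 13.3 to match.
2. Add to SAP 8.8: an SAE first documented at a visit or exam before the injection, by visit or report date, is classed as emerging before the vaccination phase, whatever its missing or partial start date. Keep the conservative default for all other incomplete dates.
3. List any recorded pre-booster SAEs separately from the booster safety tables.

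Cost: wording in both documents, one derivation rule and one listing. The visit or report date of detection must be available in the AE data. Protocol 7.1.5 does not ask for it explicitly, so this should be confirmed.
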